9.5 HEALTH ECONOMICS

Resource utilization information will be collected at each dressing change throughout the study. More specifically, investigators will provide the amount of time, in minutes, dedicated to each dressing change via a log within the electronic case report form (eCRF). Additionally, the perpatient quantity of test articles utilized will be documented according to the test article

accountability procedures of the protocol as described in Section 6.4. Non-test article wound care supplies such as spatulas, gauze, and secondary dressings are standardized for each dressing change and thus no direct documentation of utilization for these items will be collected. This information will be used to examine resource utilization rates between treatment groups.

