5. OBJECTIVE

The primary objective of this study is to compare Collagenase SANTYL® Ointment versus hydrogel in the proportion of ulcers achieving complete debridement following 6 weeks of treatment.

The secondary objectives are to compare, between groups, the time in days to complete debridement; the percentage reduction in the percentage of non-viable tissue over the 6-week treatment period and at each assessment visit; the percentage reduction in wound area over the 6-week treatment period and at each assessment visit; change in wound status as measured by the PUSH and WBS tools following 6 weeks of treatment.

The exploratory objective of this study is to determine if there is a difference in resource utilization between the two treatment groups.

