6.2 USAGE

Following normal saline irrigation, SANTYL or SoloSite (depending on treatment assignment) will be applied once daily. SANTYL will be applied directly to the entire wound bed, approximately 2 mm thick (thickness of a nickel). SoloSite will be applied directly to the entire wound bed, approximately 5 mm thick. For both treatment groups, the wound will then be covered with a semi-occlusive dressing (e.g., COVRSITETM). Should the dressing integrity be compromised due to fecal or urinary incontinence, or through inadvertent removal, additional application and dressing should be applied.

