- 7. Apply the test article to the entire wound bed according to the instructions for use located in the Study Guide, cover with a semi-occlusive dressing (e.g. COVRSITETM). If the wound has depth, saline-moistened gauze may be used to fill at the Investigator's discretion.
- Ensure that all caregivers are instructed as to the treatment requirements for the study
 protocol and that they are instructed in the application of test article and dressing changes.

Ensure adequate supplies (test article and dressings) are dispensed.

- 9. Record the time spent dressing the ulcer at this visit.
- 10. Schedule the assessment, Study Visit 2, in 7 (± 1) days.

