9.1.3 Study Visits 2-6

Study Visits 2-6 are post-randomization weekly assessments during the treatment period. During this period, all adverse events must be recorded, including those associated with treatment, study procedures, or concomitant medication. All weekly visits must be performed according to the study visit schedule (Table 17-1), preferably on the same day each week. Subjects found to have wound closure at a weekly assessment should **NOT** complete that visit but instead go directly to Study Visit 7 (Exit Visit), be discontinued from treatment and have exit procedures performed. A closed ulcer is defined as having complete re-epithelialization, without drainage or the need for a dressing. All study procedures should occur in the order outlined in the protocol. Visits occurring outside the visit window should be completed and recorded as a protocol deviation.

- If the ulcer is closed at this assessment visit, do not complete these procedures. Instead go directly to Study Visit 7 (Exit Visit).
- 2. Record any changes in general health and the use of concomitant medications.
- If any adverse events are observed or reported, they must be recorded as instructed in Section 12, Adverse Events.
- Record the number of dressing changes since the previous study visit and the amount of time spent daily dressing the ulcer.
- Irrigate the wound with normal saline delivered at 4-15 psi using the Irrimax[®] device.
 (Sharp debridement is NOT allowed.)
- Photograph the target ulcer using the ImageIQ EDCIQ mobile imaging system. The target ulcer area (cm²) and percentage of the target ulcer surface covered with necrotic,

- nonviable tissue will be determined by two independent reviewers using the ImageIQ EDCIQ mobile imaging system.
- Ensure that all caregivers are instructed as to the treatment requirements for the study
 protocol and that they are instructed in the application of test article and dressing changes.
 Ensure adequate supplies (test article and dressings) are dispensed.
- Apply the test article to the entire wound bed according to the instructions for use located in the Study Guide, cover with a semi-occlusive dressing (e.g. COVRSITETM). If the wound has depth, saline moistened gauze may be used to fill at the Investigator's discretion.
- 9. Record the time spent dressing the ulcer at this visit.
- Schedule the next weekly assessment in 7 (±1) days.

9.1.4 Exit Visit - Study Visit 7

This is the final visit for all subjects in the study.

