10.3.3 Exploratory Analysis

The exploratory analysis for this study will be a comparison of resource utilization for each treatment group. Resource utilization in the form of nursing time spent on dressing changes, test article utilization, and wound care supplies utilized will be aggregated with descriptive statistics reported by treatment group.

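### Section 9.5 leaves gauze unrecorded because it is standardized, but Sections 9.1.2 and 9.1.3 make gauze fill optional, so the supplies summary in Section 10.3.3 would omit fill

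*Combined protocol and SAP*

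**What the plan says.** The exploratory aim is set out in Section 5: "The exploratory objective of this study is to determine if there is a difference in resource utilization between the two treatment groups". Section 10.3.3 names three components of that comparison: nursing time on dressing changes, test article used, and supplies. For the last it says that "wound care supplies utilized will be aggregated with descriptive statistics reported by treatment group".

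Section 9.5 describes the data behind this. Minutes are logged in the eCRF for every dressing change, and test article quantity comes from the accountability records. For the remaining items it states that "Non-test article wound care supplies such as spatulas, gauze, and secondary dressings are standardized for each dressing change", and concludes "thus no direct documentation of utilization for these items will be collected".

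The application steps treat one use of gauze differently. At Study Visit 1 (Section 9.1.2): "If the wound has depth, saline-moistened gauze may be used to fill at the Investigator's discretion". At Study Visits 2 to 6 (Section 9.1.3): "If the wound has depth, saline moistened gauze may be used to fill at the Investigator's discretion". Section 6.2, which covers daily use, mentions only the cover dressing: "For both treatment groups, the wound will then be covered with a semi-occlusive dressing".

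**The concern.** Section 9.5 gives a single reason for not documenting gauze, namely that the amount is the same at every change. An item used only in wounds with depth, and then only if the Investigator chooses, does not meet that description. The choice is also made with the arm known: under Section 9.1.2 the Investigator or a designee obtains the assignment, and Section 8.2 says the products look too different for double-blinding.

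At stake is whether one of the three components in Section 10.3.3 describes what was used. If fill were more frequent in one arm, the planned summary would not show it. The SAP, which Section 10 says is still to be written, could not repair this, because the data would not have been collected. The stake goes no further: Section 10.3.3 specifies descriptive statistics only, with no test or decision rule.

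**Working it through.** The plan states no figure to reproduce. The check is a comparison of the text, followed by counts for scale.

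**Step 1. What is recorded.**
- Number of dressing changes since the last visit, and time spent (Sections 9.1.3 and 9.1.4).
- Minutes per dressing change, and quantity of test article (Section 9.5).
- Nursing time (Table 17-1, which has no row for supplies).

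No visit step in the supplied text records whether fill was used.

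**Step 2. What can be derived.** Let *N* be the number of dressing changes in an arm, *k* the standard gauze per change, and *F* the number of fills.
- Derivable from the plan: *k* × *N*.
- Actually used: *k* × *N*, plus the gauze for *F* fills.

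*N* is recorded, so the first quantity can be computed and may differ by arm through *N*. *F* is not recorded. The derived gauze per change is *k* in both arms, so its arm difference is *k* − *k* = 0 whatever the fill use.

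**Step 3. How many applications are open to fill.** There are 16 subjects per arm (Section 11). Section 11 also bases its calculation on 26 subjects, or 13 per arm. Counts ignore early closure, withdrawal and extra changes for compromised dressings.

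| Reading | Per subject | Arm of 16 | Both arms | Arm of 13 |
|---|---|---|---|---|
| Narrow: only where fill is stated, Study Visits 1 to 6 (Table 17-1 shows no application at Visit 7) | 1 + 5 = 6 | 16 × 6 = 96 | 32 × 6 = 192 | 13 × 6 = 78 |
| Wide (assumption): discretion extends to all once-daily changes for 6 weeks | 6 × 7 = 42 | 16 × 42 = 672 | 32 × 42 = 1,344 | 13 × 42 = 546 |

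**Step 4. Size of an unseen difference.** The documents give neither the share of ulcers with depth nor the frequency of fill. Purely as an illustration, assume that the share of changes with fill differs between arms by 0 to 25 percentage points.
- Narrow: up to 6 × 0.25 = 1.5 fills per subject, or 96 × 0.25 = 24 per arm.
- Wide: up to 42 × 0.25 = 10.5 fills per subject, or 672 × 0.25 = 168 per arm.

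The lower end is zero in both cases. The upper ends follow from the assumption and are not evidence of a difference.

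**The case against.** **Documents not supplied.** Sections 9.1.2 and 9.1.3 refer to a Study Guide, and Section 9.5 to an eCRF log. Either might hold a packing rule or a fill field. This stands, so the conclusion is confined to the supplied text. A standard quantity in the Study Guide would still not show whether fill was used, and a fill field would sit badly with Section 9.5's statement that these items are not directly documented.

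**A compatible reading.** Gauze in Section 9.5 may mean an item in a fixed kit, with fill as something separate. That would remove the contradiction in wording, but fill would still be unrecorded.

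**Indirect information.** Baseline maximum depth is a candidate covariate (Section 10.3.1), the Wound Bed Score has a depth item, and time spent filling falls within the logged minutes. These show where fill was plausible and capture its labor. None of them records fill.

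**No mechanism for an arm difference.** None is documented. Section 6.2 applies the two products at different thicknesses, about 2 mm and 5 mm, which could bear on packing, but that is inference.

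**Materiality.** This is one consumable in one of three descriptive components, and the synopsis lists the exploratory variable as not applicable. The objection stands and sets the severity.

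A reader might infer that the supplies component cannot be produced, or that the resource objective fails. The documents do not support that: the standard items follow from the recorded changes, and nursing time and test article are measured directly. A reader might also infer that open-label fill decisions bias efficacy. Nothing in the documents shows that, and the debridement photographs are assessed blinded (Section 8.2).

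**Conclusion.** The point holds in a narrow form and is minor. Section 9.5's reason for not documenting gauze does not cover optional fill. On the supplied text, the supplies summary in Section 10.3.3 would therefore omit fill and could not show whether its use differs by arm. The rest of that summary can be derived.

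The size is unknown. Fill is expressly permitted at 6 applications per subject. The count of 42 rests on extending the discretion to daily changes, which the documents do not state. No arm difference is shown, and no primary or secondary endpoint is affected. The conclusion assumes that the Study Guide and eCRF pages contain no record of fill. Confidence is medium for that reason.

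**What to change.** In Section 9.5, except optional gauze fill from the standardized supplies and add a yes/no fill field to the eCRF log already kept for each dressing change. In Section 10.3.3, report the proportion of dressing changes with fill by arm, and note that this measures frequency and not quantity.

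The cost is a wording change in two sections, one extra table row and one tick per dressing change, up to 1,344 ticks on a once-daily schedule. Limiting the field to Study Visits 1 to 6 would reduce this to 192, but would miss any fill at other changes. No visit, procedure or staff is added.

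If the field is not wanted, Section 10.3.3 should at least say that supplies are estimated as the standard set times the number of changes and exclude optional fill. That describes the table accurately but leaves any arm difference in fill unmeasured, so it does not replace the field.

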10. STATISTICAL DESIGN

A formal Statistical Analysis Plan (SAP) (also referenced to as the Statistical Considerations) will be written and finalized prior to database lock. The SAP will detail the summaries and analyses to be performed.

Smith & Nephew Wound Management Global Medical and Clinical Affairs Department will conduct data management and statistical analysis. Unless otherwise stated, all significance tests and hypothesis testing will be two-sided, performed at the 5% significance level. Resulting p-values will be quoted and 95% two-sided confidence intervals will be generated where appropriate. All analyses will be performed in SAS v9.4 (or later).

Where data summaries are specified, categorical and ordinal variables will be summarized using frequency distributions which will detail the number and percentage of subjects which fall into each category. Continuous variables will be summarized using the following summary statistics: mean, median, standard deviation, minimum and maximum values, and number of observations.

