conjunction with sharp debridement (9). In the long-term care setting, debridement with collagenase resulted in more patients achieving complete debridement, more rapidly than when a hydrogel was used (7). The goal of the present study is to confirm the results of this earlier trial, demonstrating superior debridement outcomes for pressure ulcers of patients in long-term care as compared to ulcers managed with a hydrogel.

A summary of known and potential risks and benefits to humans associated with the use of collagenase SANTYL. To ointment can be found in the Investigator's Brochure.

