10.3 EFFICACY

10.3.1 Primary Efficacy

The primary endpoint of the study is the proportion of subjects achieving complete debridement over the 6-week treatment period and will be analyzed as follows using the Full Analysis Set. For purposes of the primary analysis, the status of complete debridement will be assessed from photographs by two independent reviewers. In the event of disagreement between the two reviewers, the complete debridement status agreed during the consensus meetings will be analyzed in the primary analysis. In cases where a photograph is not taken, the Last Observation

Carried Forward (LOCF) method will be used. Sensitivity analyses will be conducted as detailed in the following sections.

An initial logistic regression model will contain covariates for treatment, baseline (defined as Study Visit 1) ulcer area, baseline percentage of nonviable tissue, and duration of ulcer. A forward selection procedure will be used for the addition of other baseline covariates with an F-value to attain a significance level of 0.1. Further baseline covariates to be assessed as part of this procedure include: subject age, baseline (maximum) ulcer depth, baseline PUSH and WBS scores.

The resulting analysis presented will correspond to the final model from the forward selection procedure. The results for the initial model will also be presented. For each of the effects in the initial and final model, the p-value, odds-ratio and corresponding 95% confidence interval will be presented. Secondary subgroup analyses may be conducted as a result of the covariate analyses. Additionally, treatment will be fitted on its own in a further logistic regression model. In each case, the residuals will be examined for outliers using influence plots of diagnostic statistics; further details are included in the SAP.

Cross-tabulations of each of the covariates (continuous covariates will be categorized for purposes of the cross-tabulations) with treatment and achievement of complete debridement, will be generated for each of the baseline covariates included in the final model.

The 95% confidence interval (unadjusted for all covariates) for the difference between treatments in proportion achieving complete debridement within 6 weeks will be generated along with the Chi-square or Fisher's Exact test p-value using the Per Protocol population depending on minimum expected cell.

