10.3.2 Secondary Efficacy

The secondary efficacy variables include the time (in days) to achieve complete debridement, the percentage reduction in non-viable necrotic tissue for each assessment visit, and the percentage reduction in ulcer area for each visit and the change in wound status as measured by the PUSH and WBS tools following 6 weeks of treatments.

Time (in days) to achieve complete debridement during the 6-week treatment period (with complete debridement as defined in the primary analysis)

Once a subject has achieved complete debridement, the time to complete debridement will be calculated from the date of the randomization visit to the date at which the subject's ulcer was deemed to achieve complete debridement:

(Date of first complete debridement visit - Date of Randomization (SV1))

For those subjects that withdraw or do not achieve complete debridement during the study, the time to complete debridement will be censored at the last visit date attended. The resulting time to complete debridement will be defined as:

(Date of Last Study Visit attended - Date of Randomization (SV1))

Where the censored time to complete debridement is greater than 42 days, this will be truncated to 42 days.

A proportional hazards survival analysis will be applied to the time to achieve complete debridement using the Full Analysis Set. An initial proportional hazards model will include the covariates for treatment, baseline (defined as Study Visit 1) ulcer area, baseline percentage of nonviable tissue, and duration of ulcer. A forward selection procedure will be used for the addition of other baseline covariates with an F-value to attain a significance level of 0.1. Further baseline covariates to be assessed as part of this procedure include: subject age, baseline (maximum) ulcer depth, baseline PUSH and WBS scores. The resulting analysis presented will correspond to the final model from the forward selection procedure. The results for the initial model will also be presented. For each of the effects in the initial and final model, the p-value, hazard-ratio and corresponding 95% confidence interval will be presented. Secondary subgroup analyses may be conducted as a result of the covariate analyses. Additionally, treatment will be fitted on its own in a further proportional hazards survival analysis.

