An initial linear regression model will contain covariates for treatment, baseline (defined as Study Visit 1) ulcer area, baseline percentage of nonviable tissue, and duration of ulcer. A forward selection procedure will be used for the addition of other baseline covariates with an F-value to attain a significance level of 0.1. Further baseline covariates to be assessed as part of this procedure include: subject age, baseline (maximum) ulcer depth, baseline PUSH and WBS scores. The resulting primary analysis presented will correspond to the final model from the forward selection procedure. The results for the initial model will also be presented. For each of the effects in the initial and final model, the p-value, parameter estimate and corresponding 95% confidence interval will be presented. Secondary subgroup analyses may be conducted as a result of the covariate analyses. Additionally, treatment will be fitted on its own in a further linear regression model. The potential for interactions will be examined by fitting the required interaction terms in addition to those effects in the final linear regression model from the forward selection procedure. In each case if the residuals are not normally distributed then non-parametric bootstrapping will be applied. If the nonparametric bootstrap estimates of the confidence intervals for the difference in mean percentage reduction in area between treatments

differ considerably to the standard model estimates, then the nonparametric bootstrap estimates will be used.

The percentage reduction in wound area over the 6-week treatment period will be summarized by treatment separately by the covariates used in the final model.

In addition, a two-sample t-test will be used to test for a difference between treatments in the mean percentage reduction in wound area between Visit 1 and Visit 2. The test will be repeated for comparisons between Visit 1 and Visits 3, 4, 5 and 6 individually. In each case, if normality assumptions do not hold, a Wilcoxon Rank Sum test will be used.

The wound area, reduction in wound area and percentage reduction in wound area at each study visit will be summarized by treatment separately by baseline wound area strata and overall.

The reduction in percentage non-viable necrotic tissue over the 6-week treatment period and at each assessment visit

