For purposes of the analysis, the assessment of percentage non-viable necrotic tissue will be assessed from photographs by two independent reviewers. The following analysis uses the mean of the two percentage non-viable tissue assessments conducted by the independent reviewers for each visit. In the event of disagreement between the two reviewers, the percentage non-viable necrotic tissue used in the following analysis will be the mean of the individual assessments of non-viable necrotic tissue after any consensus meetings have been conducted.

The reduction in the percentage non-viable necrotic tissue will be derived as:

Percentage non-viable necrotic tissue at Study Visit 1 – Percentage non-viable necrotic tissue at Study Visit 7

In cases where a photograph is not taken, the Last Observation Carried Forward (LOCF) method will be used. Sensitivity analyses will be conducted as detailed in the following sections.

The linear regression analysis described in the previous section to test for a difference between treatments in the percentage reduction in wound area over the 6-week will be repeated for the reduction in percentage of non-viable necrotic tissue over the 6-week treatment period. In addition, the separate analysis conducted to test for a difference in percentage reduction in

wound area between treatments between Visit 1 and Visits 2,3,4,5 and 6 will be repeated for the reduction in percentage of non-viable necrotic tissue at the stated time points.

The reduction in percentage non-viable necrotic tissue over the 6-week treatment period will be summarized by treatment separately by the covariates used in the final model. In addition, the percentage non-viable necrotic tissue and reduction percentage non-viable necrotic tissue at each study visit will be summarized by treatment separately by baseline percentage necrotic tissue [categorized] and overall.

Two separate sensitivity analyses will be performed to ensure that the efficacy findings are not reliant on assumptions made in the analysis, derivations or changes agreed between the blinded review panel. The previous section will be repeated with the following modifications using the Full Analysis Set only:

- The "worst case" value will be used. That is, the highest value of percentage non-viable necrotic tissue recorded by the two independent reviewers at each time point will be used for purposes of analysis.

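### Fifteen secondary between-arm tests each run at an unadjusted 5%, with no testing order and no dependence on the primary result, so secondary claims have no error control; the primary's own 5% level is intact.

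*Combined protocol and SAP*

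**What the plan says.** Section 10 (Statistical Design) states: "Unless otherwise stated, all significance tests and hypothesis testing will be two-sided, performed at the 5% significance level". It adds that p-values will be quoted. The only other significance level in the text is 0.1, and it governs covariate entry in forward selection, not any treatment comparison.

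Section 10.3.2 (Secondary Efficacy) then sets out the secondary comparisons.

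- **Time to complete debridement:** "A proportional hazards survival analysis will be applied to the time to achieve complete debridement using the Full Analysis Set".
- **Wound area over 6 weeks:** "An initial linear regression model will contain covariates for treatment" and baseline factors.
- **Non-viable tissue over 6 weeks:** the same regression "will be repeated for the reduction in percentage of non-viable necrotic tissue over the 6-week treatment period".
- **PUSH and WBS totals:** a Wilcoxon rank sum test for each.
- **Weekly wound area:** a two-sample test at Visit 2, after which "The test will be repeated for comparisons between Visit 1 and Visits 3, 4, 5 and 6 individually".
- **Weekly tissue:** the same set of weekly tests for the "reduction in percentage of non-viable necrotic tissue at the stated time points".

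On subgroups, Section 10.3.1 says: "Secondary subgroup analyses may be conducted as a result of the covariate analyses". Section 10.3.2 repeats this for time to debridement and for wound area. Interaction terms are planned in the wound-area regression, and so also in the tissue regression that copies it. None are mentioned for the logistic or Cox models.

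Section 4.1 gives the purpose: "The goal of the present study is to confirm the results of this earlier trial". Only resource use is called exploratory.

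**The concern.** A trial presented as a replication will be read for whether it confirms the earlier findings. Section 5 makes comparisons at each assessment visit part of the secondary objectives. Section 11 cites the earlier trial's weekly tissue p-values and says its secondary endpoints reached significance with similar numbers. A single significant week, or one significant score, could therefore be reported as meeting a stated objective.

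Nothing in the text makes any secondary test depend on the primary or on another secondary. If the primary missed, one or two secondary results below 0.05 could be offered as partial confirmation, and the chance of getting at least one such result by luck is well above 5%.

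The subgroup provision adds to this. A significant covariate main effect shows that the covariate is prognostic; it does not show that the treatment effect differs across its levels. As a trigger for subgroup analysis it is data-driven and poorly matched to the question.

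**Working it through.** **The plan's own figure.** The documents state no familywise error rate. Their one design figure is the 26 subjects in Section 11 for Fisher's exact test at 85% v 29%. Exact enumeration at two-sided 5% gives power of 80.9% with 13 per arm and 74.2% with 12, so 26 reproduces at an unstated 80% power. Dropout: 26/(1 - 0.15) = 30.6, which rounds up to 31, or 32 for equal arms. The trial is sized on the primary alone.

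**Count of secondary tests (Section 10.3.2).**

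- 6-week: time, area, tissue, PUSH, WBS = 5.
- Weekly: 2 measures x 5 visits (Visits 2 to 6) = 10.
- Total: 5 + 10 = 15.

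This counts distinct endpoint-by-time comparisons. It leaves out Per Protocol repeats, the initial, final and treatment-only versions of each model, and the best-case and worst-case reruns.

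**If the tests were independent.** P(at least one p<0.05) = 1 - 0.95^k.

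- Five tests: 1 - 0.95^5 = 0.226.
- Fifteen tests: 1 - 0.95^15 = 0.537.

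The expected number of false positives is 15 x 0.05 = 0.75 per trial, whatever the correlation.

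**If they are correlated.** The documents give no correlations, so these are assumptions. The model had 16 per arm, no effect, and 20,000 trials per scenario. Area and tissue were each measured at six visits, with PUSH and WBS built from the week-6 values and time built from the tissue series. A t-test stood in for every test. Visit-to-visit correlation ran from 0.5 to 0.9 (constant, or decaying with lag).

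| Cross-endpoint correlation | At least one of 15 | At least one of five 6-week tests |
|---|---|---|
| 0.3 | 29-44% | 20-21% |
| 0.5 | 26-41% | 18-19% |
| 0.7 | 22-36% | 15-16% |
| 0.8 | 19-34% | 13-14% |

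Monte Carlo error is about sqrt(0.3 x 0.7/20,000) = 0.3 percentage points.

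A simpler model with one common correlation among all 15 tests gives 46% at 0.3, 36% at 0.5, 26% at 0.7, 20% at 0.8 and 14.5% at 0.9.

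**Given a non-significant primary.** This is closer to the feared situation. A separate run used 200,000 draws of normal statistics, with the primary included at the same cross-endpoint correlation. The five-test rate was 17-20% at cross-endpoint correlation 0.3-0.5 and 9-12% at 0.7-0.8.

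**The case against.** **The primary is untouched.** A reader might infer from the blanket 5% rule that the whole trial is anti-conservative. The documents do not support that. There is one prespecified primary endpoint, and secondary tests do not inflate its level. Nor does any section say that a secondary or weekly p-value can establish efficacy if the primary fails. This stands, and it limits the point to secondary claims.

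**A separate SAP is promised.** Section 10 defers detail to an SAP to be finalised before database lock, and the 5% rule allows for exceptions. One cannot conclude that no multiplicity rule will ever exist, only that the available text neither contains one nor commits to one.

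**Correlation may be high.** PUSH gives up to 10 of its 17 points to ulcer size and 4 to tissue type. WBS scores eschar and pink wound bed. Time to debridement and percentage non-viable tissue come from the same photographs. These overlaps favour the lower rows of the table. This also stands: a firm rate such as 3 to 4 trials in 10 is tempting, but the documents cannot support it without a range.

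**Interactions are planned.** A reader might infer that effect modification is never examined. That is wrong for wound area and non-viable tissue. The gap is in the logistic and Cox models, and in the subgroup trigger, which is not tied to the interaction check.

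**Weekly comparisons are a stated objective.** Removing their p-values altogether would go further than the problem requires; a label is enough.

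**Conclusion.** The concern holds for secondary claims only. Fifteen secondary tests at an unadjusted 5%, with no order and no link to the primary, leave the chance of at least one false-positive secondary result at 54% under independence. Over the correlations assumed in the table it is roughly 20-45%. For the five 6-week endpoints alone the figures are 23% and about 13-21%. Even very high common correlation (0.9) leaves 14.5% for all 15.

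These rates assume no effect on any secondary endpoint, and every figure below the independence value rests on correlations that the documents do not give. The direction does not depend on them: any pattern short of near-perfect correlation gives more than 5%. Because the trial is framed as confirmatory, the rule should be settled before database lock.

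**What to change.** In Section 10, and carried into the SAP before database lock:

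1. Test the five 6-week secondary endpoints in the order of Section 5 (time to complete debridement, non-viable tissue, wound area, PUSH, WBS). Each is tested at two-sided 5%, and only if the primary and every earlier endpoint in the list is significant. Section 5 names PUSH and WBS in one objective, so state that PUSH comes first.
2. Report the Visit 2 to 6 comparisons as estimates with 95% confidence intervals, and label any p-value unadjusted and supportive.
3. Label any subgroup analysis descriptive. Base it on a treatment-by-subgroup interaction using the two randomised size strata in Section 8.1, and extend to the logistic and Cox models the interaction check now planned only for the linear ones.

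**Cost.** No extra subjects and no change to the primary test. The edits are short but touch Sections 10, 10.3.1 and 10.3.2. A later endpoint cannot be claimed if an earlier one misses. The logistic interaction will be fragile: if the strata split evenly (an assumption), each arm-by-stratum cell holds 8, and at 85% the chance that all eight SANTYL ulcers in a given stratum debride is 0.85^8 = 0.27. The SAP should say what will be reported if that model cannot be estimated; stratum-specific differences in proportions would serve.
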